#### **4.9 Product Replacement**

Any additional/replacement (in the case of loss or damage) of Test or Control product must be ordered by fax through Bausch + Lomb Clinical Trial Materials Management, not Customer Service, using the Bausch + Lomb Material Reorder Form.

#### **4.10 Risk Assessment**

The assessments required for the study are routinely performed and are standard of care for contact lens wearers. The subjects will be informed of any potential study specific risks in the ICF or if new risks become apparent during the study.

## 5.1 STUDY METHODS

### 5.2 Study Visits

Refer to Appendix A for a schedule of visits and parameters and Appendix B for methods of clinical evaluation.

Following identification of a potential subject, the Investigator (or designee) will explain the purpose of the study, procedures, risks/benefits, and subject responsibilities to the potential subject. The subject's willingness and ability to meet the follow-up requirements of the study will be determined. If the subject chooses to participate in the investigation, written informed consent will be obtained. The subject and the person obtaining written consent will sign and date the IRB/EC-approved ICF. Both the Investigator and subject must keep the signed ICF document. The Investigator should retain the signed original document in the subject's record, and provide a copy to the subject. In addition, the applicable privacy regulation requirements must be met.

Eligible subjects will be required to complete the following at the visits below:

Visit	Item
2-Week Follow-up Visit	Return Take Home Lens Performance Surveys. Subject may complete the second Take Home Lens Performance Survey at this visit, if not completed prior to visit
1-Month Follow-up Visit	Return remaining 2 Take Home Lens Performance Surveys (with study lenses). Subject may complete the final Take Home Lens Performance Survey at this visit, if not completed prior to visit.

#### 5.2.1 Screening Visit

**NOTE:** All VA measurements **MUST** be made using a phoropter.

After obtaining written informed consent, prospective subjects will be screened to determine whether they meet the entry criteria for the study.

Screening will proceed as follows:

- a. Enter the following information in the e-CRF :
  - subject initials
  - subject date of birth
  - screening date
- b. Collect demographic and baseline habitual lens information and record in the e-CRF:
  - The investigator or designees will ask and record the subject's responses to the Lens Performance Survey (100-point scales) regarding their experience with their habitual lens.
  - average daily wearing time
  - confirm current lens brand as Acuvue Oasys
  - current lens care products
  - habitual lens centration
  - habitual lens movement
- c. Perform the following baseline assessments (without lenses) and record in the

Study ROC2-17-014 - Protocol

e-CRF:

- spherocylindrical refraction
- distance best spectacle-corrected visual acuity (BSCVA)
- keratometry

Perform a slit lamp examination (remove the lenses if the subject wore their habitual lenses to the visit). Record the results and findings in the e-CRF.

- d. “Screen Fail” subjects are ineligible and cannot continue in the study. The reason for screen failure must be documented and maintained with a copy of their ICF.
- e. If the subject is found to be eligible, the Investigator may complete the Dispensing Visit on the same day as the Screening Visit.
- f. If lenses need to be ordered record the required information on the Material Reorder Form and schedule the subject for their Dispensing Visit on a separate day as instructed by the Sponsor.
- g. The following e-CRF should be completed.
  - Screening Visit

If the subject is discontinued or exited at this visit:

- Subject Exit

### 5.2.2 Dispensing Visit

**NOTE:** All VA measurements **MUST** be made using a phoropter.

**NOTE:** Ensure all lenses/lens types for the subject have been received prior to the Dispensing Visit.

**NOTE:** The Investigator should allow the lenses to properly settle on the eye for a minimum of 5 minutes.

If the Dispensing Visit is occurring on a separate day from the Screening Visit, perform (a) and (b) below, otherwise if the Dispensing Visit occurs on the same day as the Screening Visit, skip to (c).

- a. Perform a slit lamp examination (remove the lenses if the subject wore lenses to the visit). Record the results and findings in the e-CRF.
- b. Reconfirm subject eligibility. If the subject continues to be eligible, continue the Dispensing Visit. If the subject is determined to be ineligible, they must be discontinued and the reason recorded on the Subject Exit Form.
- c. If the subject is eligible, the unmasked designee will dispense 1 pair of the study lenses according to the unique randomization schedule provided to each site. The subject **MUST** insert the lenses.

**NOTE:** Study lenses should be allowed to equilibrate a minimum of five minutes on the eye.

Record the following into the e-CRF:

- The Investigator or designees will ask and record the subject’s responses to the

Study ROC2-17-014 - Protocol

Lens Performance Survey (100-point scales).

- dispensed lens sphere power, type, and lot number
- distance lens VA
- over-refraction and distance VA
- lens wettability
- lens centration
- lens movement

For each eye, compare the high contrast distance lens VA to the high contrast BSCVA obtained previously in the Screening Visit. If the VA has decreased by 10 letters (0.2 logMAR) or more, explain.

- g. The Investigator must assess if the lens fit and VA is acceptable.

Remind the subjects to complete the first two Take Home Lens Performance surveys after a minimum of 5 days of experience with the study lenses for each week and to return the surveys at their next visit.

- h. Subjects who meet all inclusion criteria but are found not to be eligible to participate in the study due to lens fitting characteristics at the Dispensing Visit will be exited as a non-dispensed subject.
- i. The following e-CRFs should be completed.
- Dispensing Visit

If the subject is discontinued or exited at this visit:

- Subject Exit

### 5.2.3 2-Week Follow-up Visit

*NOTE: All VA measurements MUST be made using a phoropter.*

*NOTE: If Take-Home Lens Performance Surveys are not completed upon arrival, the second week survey MUST be completed at the visit. The Investigator or designee must review the Surveys for completeness before the subject leaves the office.*

*NOTE: If the subject misses this visit, they MUST be discontinued.*

- a. Collect the following lens information from the subject:
- average daily wearing time
  - average hours of comfortable wear
  - total number of days of lens wear
- b. Complete the Symptoms/Complaints section for the subject's responses **using the Rating Scale included in initial shipment.**
- c. If the subject did not come to the visit wearing one or more study lenses, go to step e. Otherwise, evaluate the lenses (while on eye), and record the following assessments:
- The Investigator or designees will ask and record the subject's responses to the Lens Performance Survey (100-point scales).
  - distance lens VA

Study ROC2-17-014 - Protocol

- over-refraction and distance VA
- lens wettability
- lens deposits
- lens centration
- lens movement

For each eye, compare the high contrast distance lens VA to the high contrast distance lens VA obtained at the Dispensing Visit. If the VA has decreased by 10 letters (0.2 logMAR) or more, explain.

- d. Perform a slit lamp examination (remove the lenses if the subject wore lenses to the visit and place the lenses in a lens case provided filled with Bausch + Lomb Biotrue™ multi-purpose solution). Reconfirm subject eligibility. If eligible, continue the 2-Week Follow-up Visit. If the subject is determined to be ineligible, they must be discontinued and the reason recorded on the Subject Exit Form.
- e. If subject is still eligible, the subject will re-insert the study lenses (the same pair initially dispensed).

Provide subjects with the remaining two surveys and remind the subjects to complete the Take Home Lens Performance Surveys each week for the remaining two weeks. These surveys must be completed each week after a minimum of 5 days of experience with the study lenses and be returned at their next visit.

- f. If this is an Exit Visit, check the Exit Visit box and complete the Subject Exit Form. If a subject misses this scheduled follow-up visit and cannot be seen prior to the start of the visit window for the next scheduled follow-up visit, then the visit is considered missed. The missed visit box must be checked on the first page of the applicable e-CRF.
- g. The following e-CRFs should be completed.
  - 2-Week Follow-up Visit

If the subject is discontinued or exited at this visit:

- Subject Exit

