#### **3.3.1.2 Exclusion Criteria**

1. Subjects participating in any drug or device clinical investigation within two weeks prior to entry into this study and/or during the period of study participation
2. Subjects who are women of childbearing potential (those who are not surgically sterilized or postmenopausal) are excluded from participation in the investigation if they meet any one of the following conditions:
  - she is currently pregnant
  - she plans to become pregnant during the study
  - she is breastfeeding

3. Subjects with any systemic disease currently affecting ocular health or which in the Investigator's opinion may have an effect on ocular health during the course of the study.
4. Subjects using any systemic or topical medications that will, in the Investigator's opinion, affect ocular physiology or lens performance.
5. Subjects with an active ocular disease or who are using any ocular medication.
6. Subjects who are not correctable to 32 letters (0.3 logMAR) in each eye with soft spherical contact lenses.
7. Subjects who currently wear monovision or multifocal contact lenses.
8. Subjects with refractive astigmatism of 0.75 D or greater in either eye.
9. Subjects who are current Acuvue Oasys wearers who have previously been unsuccessful in wearing Acuvue Vita and/or Ultra contact lenses.
10. Subjects with anisometropia (spherical equivalent) of greater than 2.00 D.
11. Subjects with any grade 2 or greater finding during the slit lamp examination (refer to Appendix B for methods of clinical evaluation). Subjects with corneal infiltrates, of ANY GRADE, are not eligible.
12. Subjects with any "Present" finding during the slit lamp examination (refer to Appendix B for methods of clinical evaluation) that, in the Investigator's judgment, interferes with contact lens wear.
13. Subjects with any scar or neovascularization within the central 6 mm of the cornea. Subjects with minor peripheral corneal scarring (that does not extend into the central area), that in the Investigator's judgment, does not interfere with contact lens wear, are eligible for this study.
14. Subjects who are aphakic.
15. Subjects who are amblyopic.
16. Subjects who have had any corneal surgery (e.g., refractive surgery).
17. Subjects who meet any of the following criteria:
  - the subject is an employee of the investigative site
  - the subject, or a member of the subject's household, is an employee of a marketing research firm

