**NOTE: If the subject misses this visit, they MUST be discontinued.**

**NOTE: All worn and unworn lenses must be collected.**

- a. Collect the following lens information from the subject:
  - average daily wearing time

Study ROC2-17-014 - Protocol

- average hours of comfortable wear
  - total number of days of lens wear
- b. Complete the Symptoms/Complaints section for the subject's responses **using the Rating Scale included in initial shipment.**
- c. If the subject did not come to the visit wearing one or more study lenses, go to step e. Otherwise, evaluate the lenses (while on eye), and record the following assessments:
- The Investigator or designees will ask and record the subject's responses to the Lens Performance Survey (100-point scales).
  - distance lens VA
  - over-refraction and distance VA
  - lens wettability
  - lens deposits
  - lens centration
  - lens movement

For each eye, compare the high contrast distance lens VA to the high contrast distance lens VA obtained at the Dispensing Visit. If the VA has decreased by 10 letters (0.2 logMAR) or more, explain.

- d. Perform a slit lamp examination (remove the lenses if the subject wore lenses to the visit and place the lenses DRY in a lens case provided for return to the Sponsor).
- e. Fill out the Investigator Questionnaire.

*NOTE: All worn, unworn, dispensed, non-dispensed study lenses are to be returned as directed with the materials provided. Worn lenses will be returned DRY in lens cases.*

- f. The following E- CRFs should be completed.
- 1-Month Follow-up Visit
  - Investigator Questionnaire
  - The subject has completed the trial – proceed to Subject Exit.

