### 5.2.5 Exit Visit

- a. Indicate status of the subject on the Subject Exit Form. If the status is "Discontinued" or "Non-dispensed," indicate the PRIMARY (one) exit reason for each eye on the Subject Exit Form.
- b. For all subjects, complete an exit ocular examination without lenses on the eyes. Collect the following assessments:
- spherocylindrical refraction
  - distance BSCVA
  - keratometry
- c. For each eye, compare the final visit high contrast distance BSCVA to the high contrast distance BSCVA obtained at the Screening Visit. If the VA has decreased by 10 letters (0.2 logMAR) or more, explain.

- d. For each eye, compare the final visit keratometry readings to the Screening Visit keratometry readings. If there is a change of 1.00 D or more, explain.
- e. Indicate if a Post-study Follow-up Visit is required and if necessary, schedule the subject accordingly.
- f. The following e-CRFs should be completed.
  - Subject Exit

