#### Secondary Effectiveness Endpoints

- Lens performance survey (100 point scales) questions.

Study ROC2-17-014 - Protocol

- Comfort upon insertion
- Overall comfort
- Comfort at end of day

Secondary Safety Endpoints

- The proportion of subjects with any slit lamp findings grade 2 or greater at any time.

[figure not shown]
Hypotheses

The following hypotheses will be tested for each question in the take home performance questionnaire at each week.

1. The null hypothesis is that the proportion of subjects providing a response in the top three categories is equal between the treatment groups.
2. The alternative hypothesis is that the proportion of subjects providing a response in the top three categories is not equal between the treatment groups.

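### At the 2-Week and 1-Month visits, the skip for subjects who arrive without study lenses jumps over the slit lamp examination

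*Combined protocol and SAP*

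**What the plan says.** Protocol 5.2.3 (2-Week) and 5.2.4 (1-Month) share a layout. Steps a and b collect wearing time and symptoms. Step c is the on-eye lens evaluation and opens, at both visits, with "If the subject did not come to the visit wearing one or more study lenses, go to step e".

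Step d at both visits begins "Perform a slit lamp examination (remove the lenses if the subject wore lenses to the visit". At 2 weeks it also holds the reconfirmation of eligibility. Step e at 2 weeks begins "If subject is still eligible, the subject will re-insert the study lenses". Step e at 1 month is "Fill out the Investigator Questionnaire".

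The Unscheduled Visit (5.2.5.2) carries the same skip sentence, but there the lens evaluation is step d and the slit lamp examination is step e.

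The Exit Visit (5.2.5) states "For all subjects, complete an exit ocular examination without lenses on the eyes", and lists refraction, BSCVA and keratometry.

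On the analysis side, 7.2 defines the secondary safety endpoint as "The proportion of subjects with any slit lamp findings grade 2 or greater at any time". Section 7.6 compares it between groups by visit with Fisher's exact tests and rules out imputation.

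**The concern.** Followed to the letter, a subject who attends either scheduled visit without study lenses has no slit lamp examination. At 2 weeks the subject also goes straight to lens re-insertion without the eligibility check on which that step depends.

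The statistical consequence falls on the grade 2 or greater endpoint. Exclusion criterion 11 bars "Subjects with any grade 2 or greater finding during the slit lamp examination", so eligible subjects enter without such a finding. The 2-Week and 1-Month examinations are then the only scheduled post-dispensing source visible for the endpoint. A subject routed past step d has a blank result and drops out of that visit's comparison. A finding missed at 2 weeks may still be seen at 1 month. After 1 month, no later scheduled visit recovers it.

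The loss need not be random. A subject with a red or sore eye may be more likely to arrive without lenses, and that is the kind of subject the endpoint is meant to detect.

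**Working it through.** **Step-by-step comparison**

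| Visit | Step with the skip | Skip leads to | Slit lamp step | Examination reached? |
|---|---|---|---|---|
| 2-Week (5.2.3) | c | e: lens re-insertion | d | No |
| 1-Month (5.2.4) | c | e: Investigator Questionnaire | d | No |
| Unscheduled (5.2.5.2) | d | e: slit lamp | e | Yes |

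Three features of the text show a wrong letter rather than an intended exemption:

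1. Step d makes lens removal conditional on the subject having worn lenses to the visit. That condition is needed only if the examination also covers subjects who did not.
2. At 2 weeks, step e applies to subjects who are still eligible, and eligibility is reconfirmed in the step d that was skipped.
3. The same sentence works correctly in 5.2.5.2, where the lettering is one step later. That the letter was carried over between sections is an inference. The mismatch itself is in the text.

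The Exit Visit list contains no slit lamp examination, so it does not restore the one missed at 1 month.

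**Possible size**

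The plan states no figure on this point, so there is none to reproduce. The only documented input is 130 subjects per group (7.3). The other inputs are assumptions:

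- f, fraction arriving without lenses: 3%, 5%, 10%
- r1, grade 2 or greater rate in those subjects: 10%, 20%, 30%
- r0, the same rate in wearers: 2%

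Share of a visit's findings unrecorded = f·r1 / (f·r1 + (1 − f)·r0). At r0 = 2%:

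| f | r1 = 10% | r1 = 20% | r1 = 30% |
|---|---|---|---|
| 3% | 13.4% | 23.6% | 31.7% |
| 5% | 20.8% | 34.5% | 44.1% |
| 10% | 35.7% | 52.6% | 62.5% |

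Unrecorded findings per arm = 130·f·r1:

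- lowest: 130 × 0.03 × 0.10 = 0.39
- middle: 130 × 0.05 × 0.20 = 1.30
- highest: 130 × 0.10 × 0.30 = 3.90

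Middle case in full: recorded findings are 130 × 0.95 × 0.02 = 2.47, so the total is 1.30 + 2.47 = 3.77. The true rate is 3.77/130 = 2.9%. The recorded rate is 2.47/123.5 = 2.0%.

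Neutral case, r1 = r0 = 2%: the share lost equals f, that is 3% to 10%. In findings per arm this is 130 × 0.03 × 0.02 = 0.08 to 130 × 0.10 × 0.02 = 0.26.

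Sensitivity to r0 over the same grid of f and r1: with r0 = 1% the share lost is 24% to 77%; with r0 = 5% it is 6% to 40%.

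**The case against.** **Lettering.** The argument rests on step letters, and lettering elsewhere is irregular: 5.2.2 runs a, b, c and then g, h, i, and 5.2.5.2 places h before f. If the unlettered visual acuity comparison after step c had once been step d, the skip would be right. However, the letters run unbroken from a to g in 5.2.3 and from a to f in 5.2.4, and the same comparison is also unlettered in 5.2.5.2, where the skip works. A lost letter is possible but not shown.

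**Appendix A.** Section 5.2 says "Refer to Appendix A for a schedule of visits and parameters". That schedule is not in the available text and may list the slit lamp for every attending subject. If so, the examination is already required, but the schedule then conflicts with step c and the two still have to be reconciled.

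**Sites may do the right thing anyway.** The cues that reveal the error are also in front of the investigator. Symptoms are recorded at step b, before the skip. Unscheduled visits, post-study visits and adverse event reporting can catch some cases, probably including many symptomatic ones. Section 8.4 requires omissions in the e-CRF to be explained. This stands and lowers the expected loss, since the grid assumes every subject without lenses goes unexamined. It does not remove the problem. Some reportable events in 6.2 are themselves slit lamp grades (staining of grade 3 or more, neovascularization of grade 2 or more), and a later query cannot recreate an examination that was not done.

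**Magnitude.** The percentages are assumption, and the 13% to 63% range takes the rate in subjects without lenses to be 5 to 15 times that in wearers. That is fair. They illustrate what could happen and do not estimate it.

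**Conclusion.** The error is real: at two of the three visits that use this skip, it bypasses the examination that feeds the secondary safety endpoint. Confidence in the wrong reference is high. Its numerical effect cannot be determined from the documents. Under the stated assumptions it ranges from a negligible loss, if subjects without lenses are no different from wearers, to about 4 findings per arm per visit, at a point where only 2.3 to 2.5 findings per arm would be recorded. With counts that small, losing even one or two can change what a by-visit Fisher test shows.

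The consequence is limited. The rule is identical in both masked arms, so no between-arm bias is shown, and the primary take-home survey endpoints do not pass through this step. It should be fixed, but it does not threaten the trial's main comparison.

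**What to change.** Reconcile steps c to e in 5.2.3 and 5.2.4 so that the skip leads to step d, in line with 5.2.5.2, where it already reaches the slit lamp step. Confirm that Appendix A and the e-CRF skip logic agree with the corrected text.

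The cost is one letter at each of two visits and a check of the form logic. No procedure is added, because step d already provides for subjects who arrive without lenses.

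A separate query, not an error: the 100-point survey is also asked only of subjects wearing lenses at these visits, and the sponsor may wish to confirm that this is intended.

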#### 7.6 Statistical Analysis

Primary and secondary analyses will be performed on all eligible, dispensed eyes (completed and discontinued eyes pooled) for efficacy endpoints and for all dispensed eyes (completed and discontinued eyes pooled) for safety endpoints.

Questionnaire responses to the take home questionnaire will be summarized using categorical summary statistics by treatment and week. The proportion of subjects providing a response in the top three categories will be compared between treatments using chi-square tests by week. A Fisher's exact test will be used instead of a chi-square test when any cell in the contingency table has an expected count less than five.

Comfort related lens performance survey question results will be summarized using continuous summary statistics by treatment group and visit. Two-sided two-sample t-tests will be used to compare the treatment groups by visit.

The proportion of subjects with any slit lamp findings grade 2 or greater will be summarized categorically by treatment group and visit. Two-sided Fisher's exact tests will be used to compare the groups by visit.

Missing data will not be imputed.

There will be no adjustments for multiple comparisons.

There are no planned interim analyses.

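### The 100-point comfort survey sits in a step that subjects arriving without study lenses skip, so their secondary comfort scores are lost at that visit, possibly selectively

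*Combined protocol and SAP*

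**What the plan says.** Section 7.2 lists "Lens performance survey (100 point scales) questions" as the secondary effectiveness endpoints, with three items: comfort on insertion, overall comfort and end-of-day comfort. Section 7.6 compares the arms on these items visit by visit with two-sided two-sample t-tests and adds: "Missing data will not be imputed".

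Sections 5.2.3 and 5.2.4 share a layout. Steps a and b (wearing time, hours of comfortable wear, days of wear, symptoms and complaints) apply to every subject. Step c opens with a skip rule: "If the subject did not come to the visit wearing one or more study lenses, go to step e". It then continues: "Otherwise, evaluate the lenses (while on eye), and record the following assessments". The 100-point survey is the first entry in the list that follows, ahead of lens visual acuity, wettability, deposits, centration and movement.

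The survey is also asked at two earlier points. At Screening (5.2.1, step b) it concerns experience with the habitual lens, and no lens need be on the eye. At Dispensing (5.2.2) it is asked about the newly inserted study lens, with the note: "Study lenses should be allowed to equilibrate a minimum of five minutes on the eye".

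**The concern.** A subject who attends a follow-up visit without study lenses can still say how comfortable they have been. Under the written order, that subject is not asked. The missing scores concern the endpoint itself, and the reason they are missing may be related to it: someone who took the lenses out because they were uncomfortable is one plausible case. If such subjects would have scored lower, the observed mean in their arm is too high. If there are more of them in one arm, or they would have scored lower still in one arm, the between-arm difference shifts towards the arm that lost more low scores. Raising the sample size would not remove this shift, and scores not collected at the visit cannot be recovered later.

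**Working it through.** **1. Where the skip rule leads**

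| Visit | Survey in | Subject without lenses is sent to | Step d |
|---|---|---|---|
| 2-Week (5.2.3) | step c, the skipped branch | step e: re-insertion of the lenses | slit lamp, bypassed |
| 1-Month (5.2.4) | step c, the skipped branch | step e: Investigator Questionnaire | slit lamp, bypassed |
| Unscheduled (5.2.5.2) | not listed | step e: slit lamp | the skip rule itself is in step d |

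The survey is lost because it lies inside step c, so changing the letter of the destination step would not restore it. The pointer is a second matter. At both scheduled follow-up visits it passes over the slit lamp examination, which feeds the secondary safety endpoint in 7.2, whereas the same pointer at the Unscheduled Visit leads to that examination.

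**2. Whether another step recovers the scores**

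The Exit Visit (5.2.5) requires staff to "complete an exit ocular examination without lenses on the eyes" and lists refraction, best-corrected acuity and keratometry, with no survey. The Unscheduled Visit does not list it either. So nothing in the supplied text replaces that visit's scores. The Appendix A visit schedule is not in the supplied text and could not be checked.

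**3. The plan's own figure**

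The only stated operating characteristic is in 7.3 and concerns the primary endpoint: 80% power for 0.500 against 0.670 with 130 per group at two-sided 0.05. With mean proportion 0.585:

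- z = [0.17 × √130 − 1.960 × √(2 × 0.585 × 0.415)] / √(0.5 × 0.5 + 0.67 × 0.33) = (1.938 − 1.366) / 0.686 = 0.834
- Power = 0.798, which agrees with the stated 80%.

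The documents give no corresponding figure for the comfort scores.

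**4. Size of the possible bias (all inputs assumed)**

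Let f be the share of an arm arriving without lenses, and g the amount by which they would have scored below those wearing lenses (mean m). The full-arm mean is (1 − f)m + f(m − g) = m − fg, so the observed mean is too high by f × g. The between-arm bias is f₁g₁ − f₂g₂, or (f₁ − f₂) × g when the gap is common.

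| Shares, arm 1 vs arm 2 | g = 0 | g = 10 | g = 20 | g = 30 |
|---|---|---|---|---|
| 5% vs 5% | 0 | 0 | 0 | 0 |
| 5% vs 2% | 0 | 0.3 | 0.6 | 0.9 |
| 10% vs 2% | 0 | 0.8 | 1.6 | 2.4 |

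Equal shares with unequal gaps can also produce bias: at 5% in each arm with gaps of 30 and 10 points, it is 0.05 × 30 − 0.05 × 10 = 1.0 point.

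**5. Scale**

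The difference detectable with 80% power at 130 per arm is (1.960 + 0.842) × √(2/130) = 0.35 SD. That is 5.2, 7.0 and 8.7 points at assumed SDs of 15, 20 and 25.

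For the largest bias in the table (2.4 points), the scored numbers are 130 × 0.90 = 117 and 130 × 0.98 = 127.4. At SD 20 the standard error is 20 × √(1/117 + 1/127.4) = 2.56, so the shift is 2.4/2.56 = 0.94 standard errors. By normal approximation, the two-sided type I error is then 15.5% instead of 5%. It is 23.9% at SD 15 and 11.7% at SD 25. With 5% against 2% and g = 30, it is 6.5% at SD 20. With g = 0 it stays at 5%.

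**The case against.** Four points on the other side carry weight.

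- A reader might infer that these subjects are never asked about comfort with the study lens. The documents do not support that: the survey is asked at Dispensing and at any follow-up visit attended in lenses. The loss is confined to the visit in question.
- A reader might also infer that the rule does remove low scores and does favour the less comfortable lens. Nothing in the documents shows how many subjects arrive without lenses, why, or how they would score. Sections 4.1 and 4.9 foresee loss and damage, which need not be related to comfort. A between-arm bias further requires a share or gap that differs by arm.
- The primary data are intact. At the 2-Week visit, if the take-home surveys are outstanding, "the second week survey MUST be completed at the visit", with no condition on lens wear; 5.2.4 treats the final survey in the same way. Steps a and b also record comfortable hours and symptoms before the skip.
- Asking with the lens on the eye may be deliberate, as at Dispensing, and the survey wording is not in the supplied text. This counts for less, because Screening uses the survey to ask about wear experience without requiring a lens on the eye.

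It is also fair to say that moving the survey helps only subjects who attend; those who leave the study without attending still give no score. These points limit the size and certainty of the bias. They give no reason for leaving obtainable scores uncollected.

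**Conclusion.** The placement is clear from the text: at both follow-up visits a subject without study lenses is routed past the only source of the three secondary comfort scores. No other listed step recovers that visit's scores, and 7.6 neither imputes them nor plans a sensitivity analysis. That the loss is selective is plausible but not shown. Under the assumed shares and gaps, the between-arm bias runs from 0 to 2.4 points. It is small beside the detectable 5.2 to 8.7 points if few arrive without lenses. At the upper end of the assumptions it is large enough to inflate the type I error materially. The primary take-home endpoints are not touched. The change should be made because it is cheap and the loss cannot be repaired afterwards; the documents do not support saying that the comfort comparison is biased.

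**What to change.** - In 5.2.3 and 5.2.4, move the Lens Performance Survey ahead of the skip rule, alongside steps a and b. Ask it of every attending subject about wear since the last visit, before any lens evaluation.
- Record on the e-CRF whether study lenses were worn to the visit and, if not, why. State how a subject wearing only one lens is classified, since the present wording leaves this open.
- In 7.6, use all these scores in the by-visit comfort comparison and report survey missingness by arm and visit. Add a sensitivity analysis restricted to subjects who arrived wearing lenses.
- Reconcile the step e pointers across 5.2.3, 5.2.4 and 5.2.5.2, so that the documents are consistent on whether a subject without lenses goes to the slit lamp examination.

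The cost is one line moved at two visits, a short e-CRF addition and a few sentences in 7.6, with no new procedure. The small downside is that a few scores will come from recall without the lens on the eye, which the restricted analysis addresses.
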